8.3. Cardiodynamic ECG Analyses

Baseline for Cardiodynamic ECG Assessments

Baseline for the assessment of the ECG effect of CBP-307 (CBP-307 in Group 1 versus placebo in Groups 2A and 2B) will be time-matched values on Day -1.

For assay sensitivity in Groups 2A and 2B, the following baselines will be used:

- Group 2A: For moxifloxacin administered on Day 1, baseline will be Day 16, on which subjects are administered placebo. For placebo-correction in this group, placebo values will be derived from Day 15 on which subjects are administered placebo, and baseline will be obtained on Day -1.
- Group 2B: For moxifloxacin administered on Day 16, baseline will be Day 1, on which subjects are administered placebo. For the placebo-correction in this group, Day -1 values will be used as placebo (no treatment) and baseline will be obtained on Day 15.

Concentration-QTc Analysis (Primary Analysis)

The relationship between CBP-307 plasma concentrations and change-from-baseline QTcF ($\Delta QTcF$) will be quantified using a linear mixed-effects modeling approach with $\Delta QTcF$ as the dependent variable, time-matched concentrations of CBP-307 as the exploratory variate (0 for placebo), treatment (active=1 or placebo=0), and time (ie, postbaseline timepoints on Days 1, 6, and 15 categorical) as fixed effects, and a random intercept and slope per subject.⁶

The degrees of freedom estimates will be determined by the Kenward-Roger method. From the model, the slope (ie, the regression parameter for the CBP-307 concentration) and the treatment effect-specific intercept will be estimated together with 2-sided 90% CI. The estimates for the time effect will be reported with degrees of freedom and SE.

For the assessment of the ECG effect of CBP-307 versus placebo, the time term incorporated into the models (both by-time point analysis and concentration-QTc analysis [or assay sensitivity]) includes the single predose timepoint and all postdose timepoints on Days 1, 6, and 15, and Days 1 and 16 for active versus placebo and moxifloxacin versus placebo, respectively. All times are relative to the time of dosing on that day which is considered the first dose for the assay sensitivity analysis. For the analysis of CBP-307 versus placebo, the first dose of study treatment is on Day 1.

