Assay sensitivity will be demonstrated by similar concentration-QTc analysis of moxifloxacin data. If the slope of the concentration-QTc (change-from-baseline QTcF) for moxifloxacin is statistically significant at 10% level for 2-sided test and the lower bound of the 2-sided 90% CI of the predicted effect is above 5 msec at the observed geometric mean C_{max} of the 400-mg dose, assay sensitivity will be deemed to have been demonstrated.

By-Timepoint Analysis

The analysis for QTcF for CBP-307 versus placebo will be based on a linear mixed-effects model with change-from-baseline QTcF ($\Delta QTcF$) as the dependent variable, time (ie, postbaseline timepoints on Days 1, 6, and 15: categorical), treatment (therapeutic dose of CBP-307 and supratherapeutic dose of CBP-307 on Day 15, and corresponding placebo), and

time-by-treatment interaction as fixed effects. An unstructured covariance matrix will be specified for the repeated measures at postdose timepoints within subjects. If the model with unstructured covariance matrix fails to converge, other covariance matrices such as compound symmetry and autoregressive will be considered. From this analysis, the LS mean, SE, and 2-sided 90% CIs will be calculated for the contrast “CBP-307 versus placebo” for each day of Days 1, 6, and 15 at each postbaseline timepoint on Days 1, 6, and Day 15, respectively.

The by-time point analysis for QTcF will be also performed for moxifloxacin versus placebo at postbaseline timepoints on Day 1 and Day 16. A linear mixed-effects model will be used with Δ QTcF as the dependent variable and time (ie, postbaseline timepoints on Days 1 and 16: categorical), treatment (moxifloxacin and placebo), sequence (placebo/moxifloxacin or moxifloxacin/placebo), and time-by-treatment interaction as fixed effects. An unstructured covariance matrix will be specified for the repeated measures at postbaseline timepoints for subject within visit. The model will also include a subject-specific random effect. If the model with an unstructured covariance matrix fails to converge, other covariance matrices, such as compound symmetry or autoregressive, will be considered. From this analysis, the LS mean, SE, and 2-sided 90% CIs will be calculated for the contrast “moxifloxacin versus placebo” at each postbaseline timepoint, respectively.

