For HR, PR, and QRS intervals, the analysis will be based on the change-from-baseline postdose (Δ HR, Δ PR, Δ QRS). The same (by-timepoint analysis) model will be used as described for QTcF. The LS mean, SE, and 90% CI from the statistical modeling for both change-from-baseline and placebo-corrected change-from-baseline values will be listed in the tables and graphically displayed.

Categorical Analyses

The analysis results for categorical outliers, T-wave morphology, and U-wave presence will be summarized in frequency tables with counts (percentages) for both the number of subjects and the number of timepoints. For categorical outliers, the number (percentage) of subjects as well as timepoints who had increases in absolute QTcF values >450 and ≤ 480 msec, >480 and ≤ 500 msec, or >500 msec, and changes from predose baseline of >30 and ≤ 60 msec, or >60 msec; increase in PR from predose baseline $>25\%$ to a PR > 200 msec; increase in QRS from predose baseline $>25\%$ to a QRS >120 msec; decrease in HR from predose baseline $>25\%$ to an HR <50 bpm; and increase in HR from predose baseline $>25\%$ to an HR >100 bpm will be determined. For T-wave morphology and U-wave presence, the analyses will be focused on change from baseline (ie, treatment-emergent changes).

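### The CBP-307 versus placebo models use the Day -1 baseline only by subtraction; a prespecified baseline covariate would add a little precision and remove the effect of chance imbalance at almost no cost.

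*Protocol*

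**What the plan says.** Protocol Section 8.3 lists the terms of each model.

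- **Baseline.** For CBP-307 in Group 1 against placebo in Groups 2A and 2B, baseline "will be time-matched values on Day -1". It is subtracted to form the change score and has no other role in these models.
- **Primary concentration-QTc model.** The relationship "will be quantified using a linear mixed-effects modeling approach with" change in QTcF as the response. The explanatory terms are "time-matched concentrations of CBP-307 as the exploratory variate (0 for placebo), treatment (active=1 or placebo=0), and time (ie, postbaseline timepoints"; the study days covered are 1, 6 and 15. All of these enter "as fixed effects, and a random intercept and slope per subject".
- **CBP-307 by-timepoint model for QTcF.** Besides time, the terms are "treatment (therapeutic dose of CBP-307 and supratherapeutic dose of CBP-307 on Day 15, and corresponding placebo), and" their interaction; the within-subject covariance is left unstructured.
- **HR, PR and QRS.** "The same (by-timepoint analysis) model will be used as described for QTcF".
- **Moxifloxacin by-timepoint model.** The terms are time, "treatment (moxifloxacin and placebo), sequence (placebo/moxifloxacin or moxifloxacin/placebo), and time-by-treatment interaction as fixed effects", plus a subject random effect. This is a within-subject comparison in Group 2.

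The terms are enumerated in the protocol, so the absence of a baseline covariate is a stated choice and not a detail left for later.

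**The concern.** A Day -1 QTcF value contains within-subject noise, so the change from it is negatively correlated with it. Subtraction fixes the baseline coefficient at 1, while the best-fitting coefficient is smaller. Two things follow in a comparison between different subjects.

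First, the residual variance is larger than it need be, which raises the upper confidence bound that has to stay below 10 msec. Second, if Group 1 happens to start with a higher QTcF than Group 2, regression to the mean pulls its change down. That lowers the treatment-specific intercept, which enters the predicted ΔΔQTcF on both Day 6 and Day 15. An imbalance in that direction favours a negative QT conclusion; the opposite imbalance works against it.

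The random intercept per subject does not replace the covariate. It models correlation among a subject's change scores and does not take out the effect of a baseline difference between groups.

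**Working it through.** **Inputs from Protocol Section 8.1:** margin 10 msec, assumed effect 3 msec (a gap of 7 msec), SD of the change 8 msec in each group, 28 evaluable per group, 32 randomized per group, one-sided 5%, two-sample t-test.

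**Input from Appendix 6, note 5:** ten extraction timepoints per Holter day (one predose, nine postdose).

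**Assumed, not in the document:** between-subject SD σ_b of 20, 15, 10 or 8 msec, and equal within-subject variance on Day -1 and on treatment.

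**Step 1: the plan's own figure.** Noncentral t with 54 df and noncentrality 7/(8 × √(2/28)) gives power 94.38%, which agrees with the stated 94.4%. The 90% CI half-width is t(0.95, 54) × 8 × √(2/28) = 3.58 msec.

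**Step 2: precision after adjustment.** The change has variance 2σ_w² = 64, so σ_w² = 32 and σ_w = 5.66 msec. The correlation of change with baseline is ρ = −32/(8 × √(σ_b² + 32)), and the adjusted SD is 8 × √(1 − ρ²). The half-width then uses 53 df.

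| σ_b (msec) | ρ | Adjusted SD | Power | 90% CI half-width |
|---|---|---|---|---|
| 20 | −0.19 | 7.85 | 95.0% | 3.51 |
| 15 | −0.25 | 7.75 | 95.5% | 3.47 |
| 10 | −0.35 | 7.50 | 96.4% | 3.36 |
| 8 | −0.41 | 7.30 | 97.1% | 3.27 |

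The implied baseline to post-baseline correlation, σ_b²/(σ_b² + 32), runs from 0.93 at σ_b = 20 to 0.67 at σ_b = 8.

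**Step 3: shift from a 1-SE chance imbalance, 32 per group.** With baseline noise variance v, the imbalance is √(2/32) × √(σ_b² + v). The change is pulled by v/(σ_b² + v) per msec of imbalance. The product is 0.25 × v/√(σ_b² + v).

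For a single timepoint, v = 32. The primary model instead estimates one treatment intercept over all timepoints, so what matters is the noise in the subject's average over ten Day -1 values. If that noise is fully correlated across timepoints, v stays at 32. If it is independent, v = 32/10 = 3.2.

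| σ_b (msec) | Shift, fully correlated (v = 32) | Shift, independent (v = 3.2) |
|---|---|---|
| 20 | 0.25 × 32/√432 = 0.38 | 0.25 × 3.2/√403.2 = 0.04 |
| 15 | 0.25 × 32/√257 = 0.50 | 0.25 × 3.2/√228.2 = 0.05 |
| 10 | 0.25 × 32/√132 = 0.70 | 0.25 × 3.2/√103.2 = 0.08 |
| 8 | 0.25 × 32/√96 = 0.82 | 0.25 × 3.2/√67.2 = 0.10 |

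The true figure for the primary model lies between the two columns. For one by-timepoint contrast the v = 32 column applies directly.

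**The case against.** The strongest reply is that nothing is wrong with the inference. Subtracting Day -1 already adjusts for baseline, the groups are randomized, and the unadjusted contrast is unbiased over repeated randomization. The planned power does not rely on a covariate. The half-width gain is 0.07 to 0.31 msec against a 7 msec gap, and it rests on between-subject SDs that the protocol does not supply. Section 8.1 also calls its t-test calculation conservative because it ignores the gain from using all of a subject's data, so figures taken from that approximation do not measure the gain in the mixed model. All of this stands, and it makes the point one of efficiency and robustness.

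A reader might go further in three ways that the document does not support.

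- **That the primary estimate is biased.** It is shifted only conditionally on an imbalance that happens to occur.
- **That the shift in the primary model is 0.4–0.8 msec.** That is the upper extreme, with baseline noise fully shared across timepoints.
- **That every by-timepoint model is affected alike.** The moxifloxacin model compares each Group 2 subject with himself or herself, so the argument about imbalance between groups does not reach it. The 10 msec margin likewise has no bearing on HR, PR or QRS, for which no size has been computed.

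What the reply does not remove is that the improvement uses data already collected and costs almost nothing.

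**Conclusion.** The point holds as a worthwhile, low-cost improvement to the CBP-307 versus placebo models. It is not an error that threatens the conclusion. On the protocol's t-test approximation, with assumed between-subject SDs of 20 to 8 msec, power rises by 0.6 to 2.7 percentage points. In the primary model a 1-SE imbalance moves ΔΔQTcF by somewhere between 0.04 and 0.8 msec, depending on those SDs and on how strongly Day -1 noise is shared across timepoints. A 2-SE imbalance doubles the shift. The shift would matter mainly if the upper bound fell close to 10 msec, and then a covariate added after the imbalance had been seen would be open to challenge. That is the reason to settle it in advance.

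**What to change.** Prespecify before unblinding:

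- **Concentration-QTc model for CBP-307:** add each subject's mean Day -1 QTcF, centred on the overall mean, as a fixed effect. The subject mean is preferable to the time-matched value here. A covariate that varies over time beside a random intercept would mix between-subject and within-subject slopes.
- **CBP-307 by-timepoint models for QTcF, HR, PR and QRS:** add the time-matched Day -1 value of the same parameter, centred at each timepoint, and state whether its coefficient is common to all timepoints.
- **Moxifloxacin model:** no change under this point.

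The ΔΔQTcF prediction formula stays as it is. With an additive covariate the baseline term cancels from the contrast, so predicting at a particular baseline value would change nothing. The cost is about one degree of freedom in the primary model, with no new data and no change to the sample size.

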8. SAMPLE SIZE AND DATA ANALYSIS

8.1. Determination of Sample Size

Approximately 64 healthy subjects (at least 30% for each sex) will be randomized into 2 groups (Group 1 and 2) with 32 subjects in each. Group 2 consists of 2 sub-groups (Group 2A and 2B) and each sub-group will be randomized with 16 subjects.

Sample Size for Primary Analysis:

A sample size of 28 evaluable subjects per treatment group will provide more than 94.4% power to exclude that CBP-307 causes more than 10-msec QTc effect at clinically relevant plasma levels, as shown by the upper bound of the 2-sided 90% confidence interval (CI) of the model-predicted QT effect ($\Delta\Delta\text{QTcF}$) at the observed geometric mean C_{max} of CBP-307 in the study. This power is estimated approximately using a 2-sample t-test. The calculation assumes a 1-sided 5% significance level, an underlying effect of CBP-307 of 3 msec and a standard deviation (SD) of the ΔQTcF of 8 msec for both CBP-307 and placebo treatment groups. Note that this calculation is conservative, since it does not take into account any gain in precision due to the use of all data of each subject with the help of a linear mixed-effects model. The concentration-QTc analysis method is supported by Darpo et al 2015³ and Ferber et al, 2015,⁴ and consistent with the experiences from 25 recent TQT studies.

Sample Size Considerations for Assay Sensitivity:

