The geometric mean of the individual C_{max} values for CBP-307 concentrations for subjects in the active drug groups on each of Days 6 and 15 will be determined, respectively. The predicted effect and its 2-sided 90% CI for placebo-corrected change-from-baseline QTcF ($\Delta\Delta QTcF$) (ie, slope estimate \times concentration + treatment effect-specific intercept) at this geometric mean C_{max} will be obtained.

To evaluate the adequacy of model fit with respect to the assumption of linearity, the observed $\Delta QTcF$ values adjusted by population time effect estimated from the model will be used. These individual placebo-adjusted $\Delta QTcF_{i,k}$ ($\Delta\Delta QTcF_{i,k}$) values equal the observed individual $\Delta QTcF_{i,k}$ for subject i administered with active drug or placebo at timepoint k minus the estimated population mean placebo effect at timepoint k (ie, time effect). A decile plot, ie, plot of the deciles of observed concentrations and the mean placebo-adjusted $\Delta QTcF$ ($\Delta\Delta QTcF$) and 90% CI at the median concentration within each decile will be given. The regression line presenting the model-predicted $\Delta\Delta QTcF$ ⁷ will be added to evaluate the fit of a linear model and visualize the concentration-response relationship. The placebo-adjusted $\Delta QTcF_{i,j}$ equals the individual $\Delta QTcF_{i,j}$ for subject i administered with CBP-307 at timepoint j minus the estimation of time at timepoint j (ie, time effect). Additional exploratory analyses (via graphical displays and/or model fitting) will include accounting for a delayed effect (hysteresis) and the justification for the choice of PD model (linear versus nonlinear) as follows.

Criteria for Negative QT Assessment

If the upper bound of the 2-sided 90% CI of the predicted QTc effect of $\Delta\Delta QTcF$ at the observed geometric mean C_{max} on Days 6 and 15 as well as clinically relevant plasma levels is below 10 msec (ie, the upper bound of the 2-sided 90% CI at the geometric mean C_{max}

<10 msec), it can be concluded that CBP-307 does not cause clinically concerning QT prolongation within the observed plasma concentration ranges.

Investigation of Hysteresis

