2. OBJECTIVES AND ENDPOINTS

2.1. Objectives

The primary objective of the study is:

- To evaluate the effects of therapeutic and supratherapeutic CBP-307 plasma concentrations on the heart-rate corrected QT interval (QTc) in healthy subjects.

The secondary objectives of the study are:

- To demonstrate assay sensitivity of the study to detect a small QT effect using moxifloxacin as a positive control.
- To evaluate the safety and tolerability of therapeutic and supratherapeutic multiple oral doses of CBP-307 in healthy subjects.
- To assess the PK of CBP-307 following administration of therapeutic and supratherapeutic multiple oral doses in healthy subjects.
- To evaluate the effects of therapeutic and supratherapeutic multiple oral doses of CBP-307 on HR, PR and QRS intervals, and T-wave morphology.

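### Section 8.3 allows a negative QT conclusion for CBP-307 without demonstrated assay sensitivity, and says nothing about what follows if moxifloxacin misses its criterion

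*Protocol*

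**What the plan says.** All references are to the protocol; no statistical analysis plan was available.

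- **Negative-QT rule** (8.3, Criteria for Negative QT Assessment). The only condition is that the upper 90% confidence bound for the predicted CBP-307 effect stays under 10 msec. It is checked for Days 6 and 15, using each day's geometric mean peak concentration, and for plasma levels of clinical relevance. When it is met, "it can be concluded that CBP-307 does not cause clinically concerning QT prolongation within the observed plasma concentration ranges". Moxifloxacin is not mentioned.
- **Assay-sensitivity rule** (8.3, Assay Sensitivity). Two things are needed for moxifloxacin: a slope that reaches two-sided significance at 10%, and a lower 90% confidence bound above 5 msec for the effect predicted for the geometric mean peak concentration after 400 mg. If both hold, "assay sensitivity will be deemed to have been demonstrated". The text stops there, and failure is not discussed.
- **Status** (2.1). One of the secondary objectives is: "To demonstrate assay sensitivity of the study to detect a small QT effect using moxifloxacin as a positive control".
- **Sample size** (8.1). The two criteria are powered separately. For CBP-307: "A sample size of 28 evaluable subjects per treatment group will provide more than 94.4% power". For moxifloxacin: at least 95% with 28 evaluable subjects.

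No sentence in the synopsis, 2.1, 8.1 or 8.3 makes one result depend on the other.

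**The concern.** The trial aims to show that an effect is absent. Errors that shrink QT differences, such as mis-timed or mislabelled ECGs or dosing mix-ups, therefore push it towards its desired result. The moxifloxacin arm is there to show that the study can register a small effect. Under the rule as written, its result cannot change the conclusion about CBP-307.

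This is not a detail deferred to an analysis plan. The protocol states the rule under its own heading, as a sufficient condition. At stake is whether a CBP-307 bound below 10 msec can be reported as a negative study when the positive control has not shown that the study was sensitive.

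**Working it through.** **Inputs.** From 8.1: 28 evaluable subjects per group; "The calculation assumes a 1-sided 5% significance level"; "an underlying effect of CBP-307 of 3 msec"; SD 8 msec in each group; assumed moxifloxacin effect 10 msec; on-file SE 1.24 msec from another study with 24 subjects; required effect size 0.64. From 8.3: limits of 10 msec (CBP-307, upper bound) and 5 msec (moxifloxacin, lower bound).

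**1. The protocol's own figures.**
- CBP-307, two-sample t-test: noncentrality = (10 − 3) / (8 × √(2/28)) = 3.274 on 54 df; critical value 1.674; power 94.38%. The stated 94.4% reproduces.
- Moxifloxacin effect size: (10 − 5) / (1.24 × √24) = 5 / 6.075 = 0.823.
- Paired t-test, n = 28, one-sided 5%: power is 95.1% at effect size 0.64 and 99.5% at 0.823. The stated 95% reproduces.

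**2. Negative declaration without assay sensitivity, true effects as assumed.** With independence, this is P(CBP-307 passes) × P(moxifloxacin fails):
- effect size 0.823: 0.9438 × (1 − 0.9953) = 0.0044, or 0.4%;
- effect size 0.64: 0.9438 × (1 − 0.9510) = 0.0462, or 4.6%.

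Whatever the dependence, these cannot exceed the moxifloxacin failure probabilities, 0.5% and 4.9%.

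**3. Effect of attenuation (illustration).** Assume that the study registers the same fraction f of every true effect. Take a true 10 msec effect for each drug, SD 8 msec for CBP-307 and the on-file SE for moxifloxacin. The last column assumes independence.

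| f | CBP-307 passes the written rule | Moxifloxacin passes | Both |
|---|---|---|---|
| 1 | 5.0% | 99.5% | 5.0% |
| 0.8 | 23.5% | 81.7% | 19.2% |
| 0.6 | 58.0% | 21.3% | 12.4% |
| 0.5 | 74.7% | 5.0% | 3.7% |

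For f = 0.5 the registered CBP-307 effect is 5 msec, so noncentrality = 5 / (8 × √(2/28)) = 2.339 and the pass probability is 74.7%. The registered moxifloxacin effect is 5 msec, exactly at its limit, so it passes 5% of the time. Requiring both gives 0.747 × 0.05 = 3.7%.

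**4. Random noise works the other way.** At a true effect of 3 msec, power is 94.4% for SD 8, 82.7% for SD 10 and 69.5% for SD 12. At a true effect of 10 msec the pass rate is 5% for all three. Noise widens the interval and makes a negative result harder to reach.

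**5. Joint power with the gate.**
- effect size 0.64: 0.9438 × 0.9510 = 0.898; lower limit without independence 0.9438 + 0.9510 − 1 = 0.895;
- effect size 0.823: 0.9438 × 0.9953 = 0.939.

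Adding a condition cannot raise the probability of a false negative-QT conclusion, so no alpha adjustment is needed.

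**The case against.** The strongest reply is that this is mainly an omission. Nothing in the protocol says that the negative conclusion survives a moxifloxacin failure. Assay sensitivity is an objective, is powered, and has a fixed pass criterion; most readers would apply the gate unprompted, and an analysis plan could spell it out. Under the stated assumptions the problem case is rare. All of this limits the size of the point. It does not remove it, because 8.3 states a complete rule, and a gate found only in an analysis plan would differ from the protocol's criterion.

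Four stronger readings are tempting, and the document does not support them:

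- *A failed criterion means that the study could not detect 5 msec.* A moxifloxacin lower bound at or below 5 msec means that sensitivity was not shown. It does not prove insensitivity.
- *The positive control is the only safeguard.* The protocol also has supervised dosing with mouth and hand checks (5.5), measured plasma concentrations (Appendix 6), blinded central reading with the same reader and lead for each subject and cardiologist quality control (7.2.1), and model-fit and by-timepoint checks (8.3). None replaces a positive control, but they are safeguards.
- *Poor ECG reading in general favours a negative result.* Only attenuation does; step 4 shows the reverse for random noise.
- *The problem case is likely because section 1.3 gives a 6 msec mean increase for moxifloxacin.* Taking 6 msec as the effect at Cmax would give 74% to 79%. But 1.3 does not call it a peak effect, and 3.1 expects a peak of 10 to 15 msec.

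**Conclusion.** The point holds in a limited form. As written, 8.3 allows a negative QT conclusion from the CBP-307 bound alone and leaves the case of undemonstrated assay sensitivity open. The sample-size figures are correct. With a true moxifloxacin effect of 10 msec and sound measurement, the gap would be used in about 0.4% to 4.6% of trials, so this is an inexpensive repair to a decision rule and not evidence of a failed design.

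Its value lies in protection against attenuating error. The 75% figure is an illustration that rests on an assumed halving common to both drugs, not a forecast. The gate protects best against gross loss of sensitivity: at a 20% loss it lowers the false negative-QT rate only from 23.5% to 19.2%. It cannot detect an error confined to Group 1.

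The products assume independence, although Group 2 supplies both the placebo data for CBP-307 and all the moxifloxacin data. The 0.82 effect size combines an assumed 10 msec effect with another study's SE; it was not observed. The moxifloxacin powers cover the 5 msec bound, not the additional slope test.

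**What to change.** Amend 8.3, Criteria for Negative QT Assessment, so that the negative conclusion requires both assay sensitivity, as that section already defines it, and a CBP-307 upper bound below 10 msec. State that a bound below 10 msec without demonstrated assay sensitivity is reported as inconclusive.

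Optionally, add to 8.1 that joint power is about 0.90 (moxifloxacin effect size 0.64) to 0.94 (effect size 0.82), assuming independence. The component powers are already given, so this is a courtesy to the reader.

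The cost is one clause, or one clause and one sentence, and a slightly lower stated probability of success. Error control needs no extra subjects, and no dosing or clinical rule changes.
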